2.5 Multiple Testing

The primary endpoint will be tested at the 2-sided 5% significance level. No adjustments for multiplicity will be made for secondary and exploratory endpoints.

2.6 Missing Data

There are three possible sources for missing data:

1. Deaths
2. Administrative error
3. Premature study terminations

Missing data due to deaths is expected to be very low (fewer than 10 patients) because of the short follow-up period. Missing data due to administrative error is believed to be negligible due to the study management procedures and is also believed to be missing completely at random (MCAR). For patients who drop out of the study prematurely, a premature treatment discontinuation visit (PTDV) will be scheduled for them, whenever possible, to get the last assessment. The PTDV assessment will be carried forward to the next follow-up time point. For partially completed KCCQ questionnaires, the scoring algorithm accommodates a limited number of skipped responses. Values that are missing at randomization but available at screening will be imputed using the value at screening. Primary, secondary, and exploratory endpoints will be analyzed among patients for whom all relevant data for the given endpoint can be calculated.

For KCCQ scores, additional sensitivity analysis will be conducted using multiple imputation to account for missing values. IVEware (Raghunathan et al. 2002) will be used to perform the multiple imputation which employs iterative sequential regression to sample missing values from the predictive distribution of each variable, conditional on all other variables included in the imputation model. The following variables will be included in the imputation model: baseline KCCQ scores, sex, baseline eGFR, history of diabetes (DM), history of permanent AFib, baseline LVEF, baseline NYHA class, heart failure hospitalization during the trial duration, urgent heart failure visit during the trial duration, and covariates used as subgroup variables in section 2.3. Additionally, the imputation model will also include all follow up

assessments available for KCCQ scores, eGFR, NTproBNP, BNP, Hgb, loop Diuretic dose, 6-minute walk test.

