5.9.3 Procedures for permanent discontinuation of a patient from study medication

Patients permanently discontinuing study medication should be given conventional therapy, if applicable, and should continue routine care visits with their primary physician.

A patient that decides to discontinue study medication will always be asked about the reason(s) for their desire to discontinue study medication and the presence of AEs (if any). These data will be ascertained and documented by the investigator. AEs will be followed up and the patient should return all study medications.

It is essential to collect as much data as possible for all patients throughout the study and especially all potential endpoint events. Discontinuation from study medication is not the same as complete withdrawal from the study (withdrawal of consent), which has a direct impact on the potential validity of all study data, and should be avoided whenever possible.

5.9.4 Patient agrees to undergo the Premature Treatment Discontinuation Visit and then continue in-person study visits

The patient agrees to undergo the Premature Treatment Discontinuation Visit (PTDV) and then continue in-person study visits according to plan. This is the preferred option and patients who discontinue study medication will always be asked if they agree to this approach. If agreed, as above, the patient will undergo their PTDV at the next scheduled office visit after the study medication is stopped. The patient will continue attending subsequent study visits according to schedule (Table 1).

5.9.5 Patient refuses to continue in-person study visits but agrees to undergo modified follow-up

If the patient refuses to continue in-person study visits, but agrees to undergo modified follow up, the in-person PTDV visit should be performed as soon as possible after the study medication is stopped. All subsequent visits until the end of study date will be done as modified follow-ups (eg, regular telephone contacts, a contact at study closure, or other means) in order to ascertain whether any endpoints or safety events had occurred. Such a patient has not withdrawn his/her consent or withdrawn from the study.

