6.2.4 Visit 5 and 7 (office visits)

- Physical exam
- Vital Signs (seated pulse and BP and orthostatic pulse and BP)
- Weight
- Waist circumference
- Fasting blood sampling for laboratory assessments and biomarkers (biomarkers to be collected at visit 7 only)
- Urine pregnancy test (only for women of childbearing potential)
- Urine albumin/creatinine ratio
- Concomitant medications
- 6 minute walk test (at Visit 7 only)
- KCCQ questionnaire (at Visit 7 only)
- Concomitant medications
- Adverse events
- Serious adverse events
- Hospitalizations, ER visits, urgent outpatient visits for heart failure
- Volume depletion monitoring
- Ketoacidosis monitoring
- Study medication return (redispense at Visit 5) and accountability
- Contact IVR/IWR at Visit 7 for treatment completion

- Participants in echo substudy will undergo echocardiogram at the 12 week visit.

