1.3 Sample Size and Power

Planned Sample Size	Approximately 160 patients will be enrolled in each arm.
Power Statement	For the primary endpoint a sample size of 145 for each group will achieve 82% power with $\alpha=0.05$ to detect a 4.7 difference in mean KCCQ CS between dapagliflozin group and placebo group at 12 weeks. The assumptions for this calculation was derived from DEFINE-HF trial where the adjusted mean difference between dapagliflozin group and placebo group is 4.7 and the standard deviation is 13.7. Assuming a 10% loss to follow up, we arrive at a sample size of ~320 patients.

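### A study dropout's KCCQ from the premature discontinuation visit can enter the primary ANCOVA as a week-12 score, and no planned analysis clearly tests this

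*SAP*

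**What the plan says.** SAP 2.6 (Missing Data) schedules a PTDV, where possible, for patients who drop out of the study, and then states: "The PTDV assessment will be carried forward to the next follow-up time point". The rule exempts no endpoint, and the same paragraph goes on to cover the primary, secondary and exploratory endpoints.

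The related provisions are:

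- **When the PTDV happens.** Protocol 5.9.5 covers patients who refuse further in-person visits: "the in-person PTDV visit should be performed as soon as possible after the study medication is stopped". Under Protocol 5.9.4, the preferred route, the PTDV takes place at the next scheduled office visit and later visits continue.
- **When KCCQ is collected.** Protocol 6.2.6 lists KCCQ among the PTDV procedures. For the scheduled office visits, Protocol 6.2.4 has "KCCQ questionnaire (at Visit 7 only"), that is, week 12.
- **What the primary model uses.** SAP 6.1 fits an ANCOVA to the 12-week KCCQ clinical summary score. It does not repeat or modify the carry-forward rule.
- **Who is excluded.** SAP Appendix 10.2, item 6.5, removes from the KCCQ analyses only patients with no clinical summary score after randomization, so a PTDV score appears to qualify.
- **Sensitivity analyses.** SAP 2.6 plans multiple imputation for missing KCCQ scores. SAP 2.1 defines an on-treatment set that omits measurements taken while off study drug, and SAP 6.1 applies it to the primary endpoint.

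**The concern.** Together these provisions put a single-value, last-observation imputation into the primary analysis. A score taken around the time a patient stopped drug, possibly weeks before week 12, stands in for the week-12 score and carries the same weight and certainty as a measured one. The plan gives no justification for this.

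The primary estimate would then mix week-12 scores with earlier ones. The direction of any bias depends on when and why patients leave each arm, which cannot be known in advance.

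The usual safeguard would be a sensitivity analysis that replaces the carried-forward values, but the SAP does not clearly provide one. Once a PTDV score has been carried forward it is no longer missing, and the SAP does not say it is reset to missing before imputation. The imputation list also does not name treatment arm; leaving arm out tends to pull imputed arm differences toward zero.

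**Working it through.** **Inputs from the documents**

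- Significance level, SAP 2.5: "The primary endpoint will be tested at the 2-sided 5% significance level".
- Power, SAP 1.3: "a sample size of 145 for each group will achieve 82% power".
- Effect and spread, SAP 1.3, taken from an earlier trial: "the adjusted mean difference between dapagliflozin group and placebo group is 4.7 and the standard deviation is 13.7".
- Loss and total, SAP 1.3: "Assuming a 10% loss to follow up, we arrive at a sample size of ~320 patients"; "Approximately 160 patients will be enrolled in each arm".

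**1. Reproduce the plan's figures**

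Normal approximation: SE = 13.7 × √(2/145) = 1.609; 4.7/1.609 = 2.921; power = Φ(2.921 − 1.960) = 83.2%. The noncentral t with 288 df gives 82.9%. Both agree with the stated 82% to about a point.

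Total: 290/0.90 = 322.2, or 323 rounded up; 290 × 1.10 = 319. Both fit the planned total of about 320. No stated figure is wrong.

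**2. Reference case: observed week-12 scores only**

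The plan's 10% loss leaves 160 × 0.90 = 144 per arm. At 4.7 and SD 13.7, power is 82.7% (noncentral t). The power statement therefore does not depend on carry-forward.

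**3. Carry-forward applied (assumptions)**

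The documents do not say how many PTDVs to expect or when. Let L be the fraction per arm carried forward and f the share of the 4.7 effect that their PTDV scores show. The expected difference is 4.7 × (1 − L + L × f). Carried-forward patients are in the analysis, so n is 160 per arm.

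| L | f | Expected difference | Power, 160 per arm |
|---|---|---|---|
| 10% | 0 | 4.23 | 78.6% |
| 10% | 0.5 | 4.47 | 82.8% |
| 10% | 1 | 4.70 | 86.4% |
| 5% | 0.5 | 4.58 | 84.7% |

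In the 10%, half-effect case, 4.7 × 0.95 = 4.465 and power is 82.8%, against 82.7% in step 2. In the 5%, half-effect case, power is 84.7%, against 84.6% for 152 observed per arm. In both, the added patients offset the diluted effect.

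**4. Bias in one arm (assumption)**

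If 10% of one arm carries a score that differs from the true week-12 score by 5 or 10 points, the arm mean moves by 0.10 × 5 = 0.5 or 0.10 × 10 = 1.0 point. Relative to 4.7 that is 0.5/4.7 = 11% or 1.0/4.7 = 21%.

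**5. Against a treatment-policy target (assumption)**

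Suppose 10% drop out and their true week-12 effect off drug is zero. The treatment-policy effect is 0.90 × 4.7 = 4.23. Carry-forward at half effect gives 4.465, an overstatement of about 0.24. An imputation that fully restored the effect for these patients would give 4.70, an overstatement of 0.47.

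**The case against.** The strongest reply is that the affected group is small and already covered. The rule reaches only study dropouts who complete a PTDV, not everyone who stops drug. The preferred route in Protocol 5.9.4 keeps patients attending and yields a real week-12 KCCQ. Using 10% treats the whole loss allowance as carried forward, which is a ceiling under the plan's own assumption. An overstatement of 0.24 is about 0.15 of a standard error (SE = 13.7 × √(2/160) = 1.53). The on-treatment set removes PTDV scores taken off drug. The imputation model already includes all available follow-up KCCQ scores, which arguably covers the PTDV score. Finally, step 5 shows that imputation under missing-at-random can be further from a treatment-policy effect than carry-forward.

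Much of this stands. The scope is limited and the likely effect is modest. Imputation is not assumption-free, and patients with both a PTDV and a later week-12 score may be few, so the PTDV predictor may be weakly informed. What does not stand is that the planned analyses test the rule. The on-treatment set drops the affected scores rather than examining the assumption behind them, and the imputation as worded may leave them in place.

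A reader might infer two stronger points that the documents do not support.

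- **A general loss of power.** This would follow if the diluted effect were applied to 144 per arm, but that counts the dropouts twice: they would be removed as lost and also used to dilute the effect.
- **Failure of the rule to reach week 12 after an early dropout.** This follows only if the next time point means the week-6 visit. Week 12 is the only scheduled post-baseline KCCQ, so for this endpoint the natural destination is week 12. If the week-6 reading did apply, that patient's PTDV score would not enter as a week-12 score, so the two complaints cannot both hold for the same early dropout. The wording is undefined by endpoint and worth clarifying, but it is not a demonstrated failure.

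**Conclusion.** The concern holds in limited form. SAP 2.6, read with the KCCQ schedule and the primary model, allows an earlier PTDV score to be analysed as an observed week-12 score. This is inferred from the general rule, because SAP 6.1 is silent. No planned sensitivity analysis clearly replaces those scores.

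The size cannot be established from the documents. With 10% carried forward at half effect, the expected estimate falls from 4.7 to about 4.47 and there is no power loss relative to observed scores only. Power falls below that reference, to 78.6%, if the carried-forward 10% show no effect at all. The main issue is interpretation and possible bias: an arm mean could move by 0.5 to 1.0 point if 10% of one arm's scores are 5 to 10 points off, in a direction that depends on differential dropout. The stated 82% power and total of about 320 are sound. The change is worth making before unblinding; it does not undermine the design.

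**What to change.** Amend SAP 2.6 and 6.1 for KCCQ as follows.

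1. Treat an unobserved week-12 score as missing, and do not fill it with the PTDV score.
2. Use an actual week-12 score whenever one exists, including where a PTDV was also done.
3. Run the multiple imputation with treatment arm and the PTDV KCCQ named in the model. Preferably make this the primary handling; at minimum make it a sensitivity analysis in which imputed values replace carried-forward ones.
4. Keep carry-forward and complete-case analyses as sensitivity analyses.

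No new data or sample size is needed, and even a complete-case analysis keeps 82.7% power under the planned 10% loss. The cost is SAP wording plus a real change to the imputation model, since the present list does not name treatment arm. The confidence interval may be slightly wider. The primary result would also rest on a missing-at-random assumption, which could overstate a treatment-policy effect if dropouts lose benefit off drug. The SAP should state that limitation.

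### The KCCQ responder analyses have no rule that counts death as non-response: a patient who dies may be dropped, carried forward or imputed

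*SAP*

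**What the plan says.** SAP 2.6 lists three sources of missing data, with death first, and adds: "Missing data due to deaths is expected to be very low (fewer than 10 patients) because of the short follow-up period". Its general rule is: "Primary, secondary, and exploratory endpoints will be analyzed among patients for whom all relevant data for the given endpoint can be calculated".

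Three other provisions bear on a patient who dies:

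- SAP 2.1 (modified ITT set) leaves patients without evaluable follow-up data for an outcome out of that outcome's analysis.
- SAP 10.2, item 6.5, excludes patients with no post-randomization KCCQ clinical summary score from the KCCQ analyses.
- SAP 2.6 carries a PTDV assessment forward to the next follow-up time point. Protocol 6.2.6 includes a KCCQ at the PTDV.

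SAP 6.2.6 reports the proportion gaining at least 5 points by arm and fits a logistic regression. It does not mention deaths. Its sensitivity analyses are a site random effect, the on-treatment set, exclusion of high baseline scores, and multiple imputation. SAP 6.2.8 follows the same approach.

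Elsewhere the SAP does place deaths. The exploratory hierarchical score (4.3, 6.3.1) ranks them worst and keeps patients with missing KCCQ if they died.

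**The concern.** A change in KCCQ is undefined after death, but the responder question is not. A patient who died before week 12 was not alive and at least 5 points better at week 12. The complete-data rule treats this known non-response as missing.

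With unequal deaths, leaving them out flatters the arm that has more of them. The planned sensitivity analyses do not put this right. None counts death as failure, and the imputed one can turn a dead patient into a responder. What is at stake is the meaning of the responder proportions, which are secondary endpoints, and whether the handling of deaths is fixed before unblinding.

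**Working it through.** **1. The plan's own figures.** SAP 1.3 states that "a sample size of 145 for each group will achieve 82% power" for a "4.7 difference in mean KCCQ CS between dapagliflozin group and placebo group at 12 weeks", where "the standard deviation is 13.7". SAP 2.5 gives the level: "The primary endpoint will be tested at the 2-sided 5% significance level".

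- Normal approximation: 4.7 / (13.7 × √(2/145)) − 1.96 = 2.92 − 1.96 = 0.96, so power is 83.2%. The t-based value is 82.9%. Both agree with 82% to within about a point.
- "Assuming a 10% loss to follow up, we arrive at a sample size of ~320 patients": 290 / 0.90 gives 323 and 290 × 1.10 gives 319. Both agree with about 320, or 160 per arm ("Approximately 160 patients will be enrolled in each arm").
- No power or responder rate is stated for the responder endpoints.

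**2. What happens to a patient who dies before week 12.** After baseline, KCCQ is scheduled only at Visit 7 (Protocol 6.2.4) or at a PTDV (Protocol 6.2.6).

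| Situation | Main responder analysis | Multiple-imputation analysis |
|---|---|---|
| No PTDV KCCQ | Leaves numerator and denominator (SAP 2.1, 2.6, 10.2 item 6.5) | Receives an imputed week-12 score. Death is neither in the listed imputation variables nor exempted (SAP 2.6) |
| PTDV KCCQ, then death | Score could be carried forward, so could count as a responder (SAP 2.6) | Score is present, so same result |

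**3. Size.** Fewer than 10 deaths means at most 9, and 9/320 = 2.8%. I assume 145 evaluable patients per arm, and that none of the 9 has a PTDV KCCQ. Counting them as non-responders gives, in each arm,

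rate = p × 145 / (145 + deaths).

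The rates p are assumptions: 30% vs 45%, 35% vs 50%, 40% vs 55%, 50% vs 65%, and a null case of 40% vs 40% (placebo vs dapagliflozin).

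| Deaths, dapagliflozin / placebo | Change in difference over the five pairs (points) | Example, 40% vs 55%: difference (was 15.0) | Example: odds ratio (was 1.83) |
|---|---|---|---|
| 0 / 9 | +1.8 to +2.9 | 17.3 | 2.02 |
| 3 / 6 | +0.3 to +0.8 | 15.5 | 1.87 |
| 4 / 5 | −0.2 to +0.3 | 14.9 | 1.83 |
| 5 / 4 | −0.3 to −0.8 | 14.2 | 1.78 |
| 6 / 3 | −0.8 to −1.6 | 13.6 | 1.74 |
| 9 / 0 | −2.3 to −3.8 | 11.8 | 1.61 |

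Check of the last row: 0.55 × 145/154 = 51.8%, and 51.8 − 40.0 = 11.8.

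With a smaller assumed effect, 37% vs 45%, the 8.0-point difference becomes 8.6 (3 / 6), 9.1 (2 / 7) or 7.5 (5 / 4).

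**4. Diabetes subgroup.** SAP 6.2 repeats the secondary analyses by diabetes status, and Protocol 12.2 plans 58 per arm with diabetes. At 37% vs 45%:

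- 4 / 1 deaths: 0.45 × 58/62 − 0.37 × 58/59 = 42.1 − 36.4 = 5.7 points.
- 1 / 4 deaths: 0.45 × 58/59 − 0.37 × 58/62 = 44.2 − 34.6 = 9.6 points.

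**5. Carry-forward.** Each patient counted as a responder on a PTDV score who then died adds 1/145 = 0.7 points to that arm's rate.

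**The case against.** The strongest objection is size. At 37% vs 45% with 145 per arm, the standard error of the difference is √[(0.45 × 0.55 + 0.37 × 0.63)/145] = 5.8 points. Shifts of 0.5 to 1.1 points are therefore 0.1 to 0.2 standard errors. The endpoints are secondary, without multiplicity control. Nine deaths is a ceiling, against 32 patients at the planned 10% loss (0.10 × 320). All of this stands and makes the point minor.

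Next, counting death as failure is one estimand among several, and the SAP already joins death with KCCQ in the hierarchical score and compares deaths by arm (SAP 7). This stands in part. A reader would see a mortality imbalance, but the hierarchical score is a separate exploratory endpoint and does not correct the responder proportions. The SAP does not state or justify another strategy for deaths in 6.2.6.

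A reader might also draw stronger conclusions that the documents do not support:

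- *That the responder rate is conditional on survival.* Because of the PTDV carry-forward, it is conditional on having a calculable score.
- *That the SAP expressly drops or imputes deaths in 6.2.6.* It does not. Both results follow from general rules.
- *That the same argument covers 6.2.7.* That endpoint is NT-proBNP only and the planned imputation is for KCCQ scores. A week-6 value may also be observed before a later death.
- *That the rule favours dapagliflozin.* The direction depends on where the deaths fall.

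**Conclusion.** The point holds for 6.2.6 and 6.2.8. The general rules treat a known non-response as missing, may credit a patient who later died with an earlier PTDV score, and allow a hypothetical score in the sensitivity analysis.

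The expected effect is small: under 1 point for a near-even split of 9 deaths, and up to about 4 points (3.8 in the table) if all fall in one arm. These figures rest on the SAP's ceiling for deaths, 145 evaluable patients per arm, and responder rates that are assumed. Shifts can be larger in the diabetes subgroups. The primary endpoint and its power are not affected. This is a low-priority improvement, worth making because it is cheap and best settled before unblinding.

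**What to change.** - **SAP 6.2.6 and 6.2.8:** count death before the week-12 KCCQ as non-response in the main and the imputed responder analyses, overriding any carried-forward PTDV score. In 6.2.8 this covers both NT-proBNP time points, because each combination needs the week-12 KCCQ.
- **SAP 2.6:** state that KCCQ is not imputed after death for these endpoints.
- **SAP 6.2.7:** if the rule is extended here, apply it only to deaths before the relevant NT-proBNP time point. A blanket rule of death before week 12 would overwrite an observed week-6 result.

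The cost is a few sentences and no new data. Vital status is already sought, even after withdrawal of consent (Protocol 5.9.6 and 5.10.1), and reported (SAP 3.2). The downside is that responder rates fall by about 1 to 2 points at the ceiling: with 4 or 5 deaths in an arm, 40% becomes 38.9% or 38.7%, and 65% becomes 63.3% or 62.8%.

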2.3 Strata, Covariates, and pre-specified subgroup analyses

All efficacy and safety endpoints will be analyzed in the entire cohort, and then within the subgroups of patients with and without diabetes. Analyses for the primary and secondary endpoints will be adjusted for the corresponding baseline measurements as well as sex, eGFR, diabetes (DM), permanent AFib, and LVEF. Restricted cubic splines will be used for continuous variables to accommodate non-linear effects, as appropriate.

A sensitivity analysis will repeat the primary analysis but will also include site as a random effect to account for potential clustering by enrolling centers. Another sensitivity analysis for the primary endpoint will be performed using the imputed KCCQ values as described in section 2.6.

Additionally, the following pre-specified subgroup analyses will be performed for the primary endpoints (stratified by the baseline variables below):

- Baseline NTproBNP (< median, \geq median)
- Baseline LVEF (\leq 60%, $>$ 60%)
- Atrial fibrillation type (No AFib, permanent/persistent AFib, paroxysmal AFib)
- Baseline KCCQ overall summary score (<median, \geq median)
- Baseline eGFR ($<$ 60, \geq 60 mL/min/1.73 m²)
- Age ($<$ 70, \geq 70)
- Sex (male, female)
- Race (white, non white)
- BMI(<median, \geq median)

- Furosemide equivalent mean daily dose: ≤ 40 mg, >40 mg
- NYHA Class (II, III or IV)

Subgroup analyses will be carried out by augmenting the primary analysis model with terms for subgroup and a subgroup-by-treatment interaction. Adjusted point estimates and 95% confidence intervals will be calculated for the effect of dapagliflozin compared with placebo within each subgroup. An interaction p-value will be provided.

Due to the large number of study sites and the expected low number of patients per site, site effects will not be explored, although study site will be included as a random effect in efficacy sensitivity analyses to account for within-site correlations, as specified above.

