4.3 Exploratory Outcome Variables

- Composite mean hierarchical-rank clinical score.

All patients will receive a global rank endpoint based on time to death (tier 1), time to HF hospitalization or urgent HF visit (tier 2), or change in KCCQ clinical summary score from baseline to 12 weeks. The variable for ranking the patients will be derived as follows.

- Patients dying during the study will have a value of $0 + (\text{study days from randomization to death})$. Patients with missing vital status at the end of trial will be excluded from the analysis. Patient dying during the study but with no mortality date will use the average of the last known alive date and the patient's scheduled 12 weeks follow-up date.

- Patients who did not die but had multiple occurrences of HF hospitalization or urgent HF visit will have a value of 200 – number of occurrences.
- Patients who did not die but have only one HF hospitalization or urgent HF visit will have a value of 200 + (study days from randomization to the occurrence of HF hospitalization or urgent HF visit). Patients known to have an event but event date is unknown will be imputed using the median rank based on the rank of other patients in this category.
- Patients who did not die and did not experience HF hospitalization or urgent HF visit will have a value of 400 + (change in KCCQ clinical summary score from baseline to week 12).

Patients with missing KCCQ at 12 weeks who didn't die and didn't have HF events will be excluded. A sensitivity analysis will be performed where these patients will be kept in the analysis and the KCCQ values will be imputed using multiple imputation as described in section 2.6.

- Number of heart failure hospitalizations and proportion of patients experienced heart failure hospitalizations
- Number of urgent heart failure visits and proportion of patients with urgent heart failure visits
- Total number of heart failure hospitalizations and urgent heart failure visits and proportion of participants who experienced any heart failure hospitalizations and urgent heart failure visits.

For the four endpoints above, only events positively adjudicated by the clinical event committee will be included. Events that occurred between screening and randomization, and between 12 weeks and 13 weeks will be excluded from this analysis. Events that occurred between the week 12 and week 13 study visits will be reported in a separate, supplemental analysis.

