6 EFFICACY ANALYSES

6.1 Analysis of the Primary Efficacy Endpoint

Analysis of the primary efficacy endpoints will be performed on the modified ITT data set, first on the entire cohort, then within the subgroups of patients with and without diabetes, and then within other subgroups as specified in section 2.3. Sensitivity analyses will be performed as outlined in section 2.3; in addition, supportive analyses will be repeated using the same models on the on-treatment set (OTS) and per-protocol set (PPS), as applicable.

Mean, standard deviation, median, and interquartile range (IQR) will be reported for KCCQ clinical summary score and for its change at 12-week follow-up, for the entire cohort and by treatment group.

An ACCOVA model will be used to estimate the effect of dapagliflozin on the 12-week KCCQ clinical summary score, adjusting for baseline KCCQ clinical summary score, sex, eGFR, Diabetes status, permanent atrial fibrillation status, and LVEF. Patient participation in the Echocardiography sub-study will not be controlled for because we don't hypothesize that participation in the Echocardiography sub-study is associated with the primary outcome (KCCQ CS).

A sensitivity analysis will repeat the primary analysis but will also include site as a random effect to account for potential clustering by enrolling center. Another sensitivity analysis will be performed using the imputed KCCQ values as described in section 2.6.

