6.2.5 HbA1c at 6 and 12 weeks

HbA1c at 6 and 12 weeks will be analyzed in a manner analogous to that of NT pro-BNP, although appropriate distributions and link functions will be chosen for the given outcomes. Models will also provide separate effect estimates for the 6- and 12-week time points

6.2.6 Proportion of patients with a \geq 5pts increase in KCCQ clinical summary score and KCCQ overall summary score at 12 weeks

Proportion of patients achieving a \geq 5pts increase in KCCQ clinical summary score at 12 weeks

Unadjusted proportion of patients achieving a \geq 5pts increase in KCCQ clinical summary score at 12 weeks, will be reported for the treatment group and placebo group. A logistic regression model will be used to assess the treatment effect. Model will be adjusted for baseline measurement, sex, eGFR, diabetes (DM), permanent AFib, and LVEF. Several sensitivity analyses will be performed:

- Repeat the model above but also include site as a random effect to account for potential clustering by enrolling center.
- Repeat the model above on the on-treatment set (OTS).
- Repeat the model above excluding patients with baseline KCCQ clinical summary score of over 90 (as these patients will have a limited opportunity for improvement in KCCQ)
- Repeat the analysis using the imputed KCCQ values as described in section 2.6.

Proportion of patients achieving a \geq 5pts increase in KCCQ overall summary score at 12 weeks

Proportion of patients achieving a \geq 5pts increase in KCCQ overall summary score at 12 weeks will be analyzed in a manner analogous to that of proportion of patients achieving a \geq 5pts increase in KCCQ clinical summary score at 12 weeks.

6.2.7 Proportions of patients with a \geq 20% decrease at 6 and 12 weeks NTproBNP

This end point will be analyzed in a manner analogous to 6.2.6.

6.2.8 Proportions of patients with a \geq 5pts increase in KCCQ and a \geq 20% decrease in 6 and 12 weeks NTproBNP

This end point will be analyzed in a manner analogous to 6.2.6. Proportion will be calculated for patients with a \geq 5 pts increase in KCCQ and a \geq 20% decrease in NTproBNP at 6 weeks, and separately for patients with a \geq 5 pts increase in KCCQ and a \geq 20% decrease in NTproBNP at 12 weeks.

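### The KCCQ multiple-imputation model in SAP 2.6 leaves out randomised treatment, so the missing-data sensitivity analyses are pulled toward no difference

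*SAP*

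**What the plan says.** SAP 2.6 specifies multiple imputation in IVEware by sequential regression, with each missing value drawn "conditional on all other variables included in the imputation model". It then names the variables: "The following variables will be included in the imputation model: baseline KCCQ scores, sex, baseline eGFR, history of diabetes (DM), history of permanent AFib". The list goes on to ejection fraction and NYHA class, both at baseline, and then to "heart failure hospitalization during the trial duration, urgent heart failure visit during the trial duration, and covariates used as subgroup variables in section 2.3". A last sentence adds all follow-up "assessments available for KCCQ scores, eGFR, NTproBNP, BNP, Hgb, loop Diuretic dose, 6-minute walk test".

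Treatment arm is in neither part. It cannot come in through SAP 2.3 either, because those subgroups are defined on baseline characteristics: "the following pre-specified subgroup analyses will be performed for the primary endpoints (stratified by the baseline variables below". They are NT-proBNP, LVEF, AF type, KCCQ overall summary, eGFR, age, sex, race, BMI, diuretic dose and NYHA class.

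The imputed scores are used in three places:

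- the primary endpoint (SAP 6.1): "Another sensitivity analysis will be performed using the imputed KCCQ values as described in section 2.6";
- the 5-point responder endpoints (SAP 6.2.6): "Repeat the analysis using the imputed KCCQ values as described in section 2.6";
- the hierarchical composite (SAP 4.3): "the KCCQ values will be imputed using multiple imputation as described in section 2.6".

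**The concern.** Each of these analyses estimates a dapagliflozin-versus-placebo effect, so the analysis model contains treatment and the imputation model does not. The two are uncongenial. A dapagliflozin patient and a placebo patient with the same listed covariates receive imputed scores from the same distribution, so the imputed part of the data contributes no direct treatment difference. If the drug works, dapagliflozin patients with missing scores are imputed too low and placebo patients too high.

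This is the only specified analysis that tests the primary result against missing KCCQ scores. The random-site model and the on-treatment and per-protocol sets do not restore missing scores. If significance were lost under imputation, nobody could tell whether the result was fragile to missing data or the imputation model had diluted it.

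**Working it through.** **Inputs.** From SAP 1.3: difference 4.7, SD 13.7, 145 evaluable per arm for 82% power, 10% loss, about 160 enrolled per arm. From SAP 2.5: two-sided 5% test.

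**The plan's own figure.** The standard error is 13.7 × √(2/145) = 1.609, and 4.7/1.609 = 2.921. Power is Φ(2.921 − 1.960) = 83.2%, or 82.9% with the noncentral t, against the stated 82%. For loss, 290/0.90 gives 323 and 290 × 1.10 = 319, against about 320. The inputs reproduce.

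**Expected dilution.** Let a fraction m be missing completely at random in each arm, and let no imputation variable carry treatment information. Observed patients contribute the full difference Δ and imputed patients contribute none, so the expected estimate is Δ(1 − m):

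- m = 5%: 4.7 × 0.95 = 4.47
- m = 10%: 4.7 × 0.90 = 4.23
- m = 20%: 4.7 × 0.80 = 3.76

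**Simulation.** 2,000 trials per scenario, 160 per arm, residual SD 13.7, 20 imputations, Rubin's rules, ANCOVA on baseline and arm. Assumed: baseline mean 60 and SD 20, slope 0.7 on baseline, missing completely at random.

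| Missing | True effect | Estimate, arm included | Estimate, arm omitted | Rejection, included | Rejection, omitted | Rubin SE / empirical SD, omitted |
|---|---|---|---|---|---|---|
| 5% | 4.7 | 4.74 | 4.49 | 84.3% | 81.7% | 1.57 / 1.49 |
| 10% | 4.7 | 4.69 | 4.21 | 82.5% | 76.6% | 1.62 / 1.44 |
| 20% | 4.7 | 4.73 | 3.77 | 78.2% | 62.1% | 1.70 / 1.40 |
| 10% | 0 | −0.03 | −0.02 | 4.9% | 3.4% | 1.61 / 1.46 |

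The simulated estimates agree with the formula. With arm omitted, the Rubin standard error is also larger than the true sampling SD, which makes the test conservative. When the true effect is zero the estimate is unbiased.

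**Allowing for the listed follow-up variables.** Add one follow-up variable that is always observed, correlates 0.3 with the KCCQ residual, and is itself shifted by treatment (all assumed). At 10% missing and still without arm, the estimate is 4.35 for a shift of 0.3 SD and 4.51 for a shift of 0.6 SD. That recovers (4.35 − 4.21)/(4.69 − 4.21), about 29%, and (4.51 − 4.24)/(4.72 − 4.24), about 55%, of the loss (the second scenario's own values without and with arm are 4.24 and 4.72). Both stay below 4.7.

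**The case against.** The best case for leaving this alone has five parts.

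**Only sensitivity analyses are touched, and the error is conservative.** True. The primary ANCOVA uses available scores, and pooled imputation does not manufacture a false positive: rejection under the null was 3.4%. This limits the consequence, but a sensitivity analysis that is biased by construction does not do its job.

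**The listed post-baseline variables carry treatment information.** Partly true, and the check above credits it. Week-6 NT-proBNP, BNP and renal results are scheduled, so patients lost after week 6 would normally have them. However, KCCQ and the walk test are scheduled after baseline only at week 12 or at the premature discontinuation visit. Protocol Appendix D also allows weeks 6 and 12 by phone, with procedures that cover events and concomitant medication but no KCCQ, laboratory tests or walk test.

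**Little may need imputing.** Possible. A KCCQ score from the discontinuation visit is carried forward, and few deaths are expected. SAP 10.2 item 6.5 excludes patients with no post-randomisation KCCQ from the ITTS KCCQ analyses; whether this also governs the imputation analysis is not stated. The 10% is the plan's loss assumption, and 20% is purely illustrative.

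**The shift is small.** At 10% missing it is 0.48 point against a standard error of 1.62, about 0.3 of a standard error. That is fair as a statement of size.

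**Treatment may be implied.** Elsewhere the SAP lists adjustment covariates without repeating treatment, but those sentences describe models whose stated purpose is to estimate a treatment effect. SAP 2.6 has no such wording, and a programmer following it would leave arm out. It also gives no sign of a deliberate reference-based assumption; such a method would move dapagliflozin dropouts toward placebo, whereas pooling moves placebo dropouts toward dapagliflozin as well.

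**Conclusion.** The imputation model is wrong as written. If a true effect exists, every sensitivity estimate built on it is attenuated by up to about the fraction imputed: about 0.5 point of 4.7 at the plan's 10% loss, about 0.2 at 5% and about 0.95 at 20%. These figures assume values missing completely at random at equal rates in both arms and no informative follow-up variables, so they describe the full dilution. One treatment-responsive follow-up variable of moderate strength brings the 10% estimate back to 4.35–4.51. The primary analysis stands, and the error cannot create a spurious benefit. What is lost is the ability to read the missing-data sensitivity analysis as evidence for or against the robustness of the primary result.

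**What to change.** In SAP 2.6, add randomised treatment arm to the imputation variables, or state that imputation is done separately within each arm. In the same edit, say whether patients excluded under SAP 10.2 item 6.5 are included in the imputation analysis. If a no-effect assumption for dropouts is wanted, specify it as a separate, named reference-based analysis. Make the change before unblinding, so that adding arm is not a post hoc departure. The cost is a phrase or two in the SAP and one line of IVEware code, with no change to data collection, sample size or the primary model.
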